minute applications for both groups in accordance with the manufacturer's directions. The bleaching agent was refreshed every 8 minutes during the 24-minute application period. At the end of each session, a single researcher responsible for the blinding [name] delivered a single syringe to the operator, which would contain desensitizing gel if the patient was in the control group, or placebo gel containing only carbopol (no active ingredient) if the patient was in the dexamethasone group. The gel was applied with a brush on the labial surface of the whitened teeth for 2 to 3 minutes as the manufacturer (Soothe SDI Dental Limited) directed. Two bleaching sessions were performed 1 week apart.

TS evaluation: TS was evaluated during bleaching and up to 1 hour, 24 hours and 48 hours postbleaching. The volunteer was asked to indicate the numeric value of the degree of sensitivity for each of the periods above, using a 5-point numeric rating scale (NRS) in which 0= none, 1= mild, 2= moderate, 3= considerable and 4= severe [2,4,5,7,23].

In addition, the volunteers were also instructed to record the pain intensity using the visual analogic scale (VAS) [3,6-9]. This scale is a 100-milimeter horizontal line with scores of 0 and 100 at their ends, in which 0 = no sensitivity and 100 = severe sensitivity. The volunteer had to mark with a vertical line across the horizontal line of the scale the intensity of the TS. Then, the distance in millimeters from the zero ends was measured with the aid of a millimeter ruler.

The data from each bleaching session were evaluated separately and were merged. For this purpose, the worst score or numeric value obtained in both bleaching sessions was considered for statistical purposes and the determination of the overall risk and intensity of TS.

If the volunteer scored 0 (no sensitivity) in all time assessments from both bleaching sessions, this volunteer was considered to be insensitive to the bleaching protocol. In all other circumstances, the volunteers were considered to have sensitivity stemming from the bleaching procedure. This dichotomization allowed us to calculate the absolute risk of TS, which represented the percentage of volunteers who reported TS at least once during treatment. We also calculated the overall TS intensity.

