## Statistical analysis

We performed the analysis after the intention-to-treat protocol, and we involved all participants who were randomly assigned [21]. In cases of missing data, the last observation was carried forward. The statistician was masked to the study groups. The absolute risk of TS and its intensity were evaluated by using Fischer's exact test. ( $\alpha = 0.05$ ). The authors calculated the relative risk as the confidence interval for the effect size.

Comparison of the TS intensity (NRS data) of the 2 groups at the 2 different assessment points were performed by using the Mann-Whitney U test, and comparisons between times within each group were performed using the Friedman test. The comparisons of the TS intensity obtained with the VAS scale were evaluated by using a 2-way repeated measures ANOVA and Tukey's test.

Color changes between groups ( $\Delta$ SGU between base line versus 1 week after the 2nd bleaching session) were compared by using a t test, and the shade changes were evaluated by using Student's t test. In all statistical tests, the significance level was 0.05. We performed all analyses by using the software SPSS for windows version 20.0 (IBM).

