#### Results

We screened 123 participants examined in the dental chair to check if they met the inclusion and exclusion criteria (Figure 1). The bleaching procedures were implemented exactly as planned and no modification was performed.

Characteristics of included participants: The baseline color of the volunteers was similar (control group: 5.9 [1.9]; dexamethasone: 5.6 [2.1]); the mean age (SD) between volunteers was similar between the groups (control: 22.5 [2.1] and dexamethasone: 22.3 [2.7]), ranging from 19 to 29 years. Thirty-four percent of the volunteers from the control group, and 23% of the volunteers from the dexamethasone group were men.

*Protocol adherence and dropouts*: No discontinuity in both treatment groups was found in the clinical investigation. All volunteers attended the recall visit 1 week postbleaching.

*Tooth Sensitivity*: Two volunteers, 1 from each group, took an analgesic to alleviate the bleaching-induced TS (Tylenol, Janssen Cilag Farmacêutica) in the period from 5 to 7 hours after the 2nd and last clinical bleachings.

Table 2 shows the number of participants who experienced TS during the bleaching regimen in the control group and dexamethasone group. In this table, it is shown that no significant difference was observed between groups (p = 0.075). The relative risk, along with the 95% confidence interval, is also evidence that the use of the experimental drug protocol had no effect on the reduction of TS.

Tables 3 and 4 show that the TS was similar in both groups, at different assessment points, in both sessions, using both pain scales. It is also seen that the bleaching-induced TS did not last longer than 48 hours after the bleaching protocol (Tables 3 and 4).

Color Evaluation: Significant whitening was observed in both groups (P < .001). The descriptive data from bleaching obtained after the 1st and 2nd bleaching sessions can be seen in Table 5. At the end of the bleaching protocol, a whitening of approximately 3 shade guide units was detected for both groups.

The results of the subjective shade evaluation (VITA Classical: P = 0.27; VITA Bleachedguide 3D-MASTER: P = 0.68) matched the hypothesis of equality between the groups after bleaching. The effect size and the confidence interval for the overall mean difference is also shown in Table 5 and is evidence of no statistical difference between groups.

Adverse effects: In this study, no reports of adverse effects by volunteers were received.

TABLE 1

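### Similar tooth-sensitivity intensity is concluded from 16 pointwise NS labels, while the overall worst-score intensity and the ANOVA group result are not reported

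*Combined protocol and SAP*

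**What the plan says.** Under TS evaluation (Materials and Methods), sessions are analysed separately and also merged. For the merged data, "the worst score or numeric value obtained in both bleaching sessions was considered for statistical purposes", and this is to give both the overall risk and the overall intensity. The same subsection ends: "We also calculated the overall TS intensity".

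The Statistical analysis section then gives three statements on intensity:
- Overall: "The absolute risk of TS and its intensity were evaluated by using Fischer's exact test".
- NRS: the between-group comparisons at assessment points "were performed by using the Mann-Whitney U test".
- VAS: the comparisons were "evaluated by using a 2-way repeated measures ANOVA and Tukey's test". The factors are not named, and it is not said whether session is one of them.

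The Results report overall risk (Table 2) and then state that "Tables 3 and 4 show that the TS was similar in both groups", a statement made for the separate assessment times, for each session and for each scale. Tables 3 and 4 mark every between-group comparison NS. No overall intensity, ANOVA group or group-by-time result, p-value, difference or interval is given for intensity. No equivalence margin is stated.

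**The concern.** A non-significant test says that a difference was not detected, not that the groups are alike. Similarity needs an interval narrow enough to exclude differences that matter. Here no interval is shown, and the two summaries that address intensity as a whole are missing.

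This matters because the control arm received an active desensitizing gel. A reader may take the sentence to mean that the two regimens can be treated as equal for pain intensity. The sample size was set for the binary risk only (90% versus 60%), so nothing in the design supports such a reading for intensity.

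**Working it through.** **Inputs.** Means and SDs from Table 4; 35 per arm from Table 2 (33 + 2 and 28 + 7); no dropouts (Results). The within-person correlation r is not given and is assumed.

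**Step 1: the reported labels.** Each of Tables 3 and 4 has 4 times × 2 sessions = 8 comparisons, so 16 in all, every one NS. Table 5, by contrast, gives p-values, differences and 95% CIs for colour.

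**Step 2: reproducing the VAS labels.** The ANOVA and Tukey tests cannot be rerun without individual data. As an approximation I used unadjusted two-sample t tests, with SE = √[(SD_C² + SD_D²)/35] and CI = difference ± 1.9955 × SE (68 df). Example, session 2 during bleaching: SE = √[(21.39² + 6.34²)/35] = 3.77 and t = 7.57/3.77 = 2.01.

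| Session, time | Control − dexamethasone (mm) | 95% CI | p |
|---|---|---|---|
| 1, during | 0.58 | −7.19 to 8.35 | 0.88 |
| 1, 1 h | 4.83 | −3.20 to 12.86 | 0.23 |
| 1, 24 h | 3.20 | −2.43 to 8.83 | 0.26 |
| 1, 48 h | 2.54 | −0.59 to 5.67 | 0.11 |
| 2, during | 7.57 | 0.04 to 15.10 | 0.049 |
| 2, 1 h | 6.74 | −1.43 to 14.91 | 0.10 |
| 2, 24 h | 6.83 | −3.22 to 16.88 | 0.18 |
| 2, 48 h | 0.77 | −1.61 to 3.15 | 0.52 |

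The labels are broadly reproduced. The one borderline point gives p = 0.049 pooled and 0.052 by Welch, and a Tukey adjustment could also make it NS. All eight differences have the same sign. The intervals reach 12.9 mm (session 1) and 16.9 mm (session 2), against control means of 1.9 to 16.6 mm.

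**Step 3: overall VAS contrast.** Control 77.25/8 = 9.66 mm; dexamethasone 44.19/8 = 5.52 mm; difference 33.06/8 = 4.13 mm.

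Variance of a volunteer's mean of eight scores = [ΣSD² + r((ΣSD)² − ΣSD²)]/64. For control, ΣSD = 128.31 and ΣSD² = 2317.33. For dexamethasone, ΣSD = 84.45 and ΣSD² = 1165.49.

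At r = 0.5 the variances are 146.72 and 64.82, so SE = √[(146.72 + 64.82)/35] = 2.46 and t = 4.13/2.46 = 1.68. At r = 0.8 they are 213.03 and 92.79, so SE = 2.96 and t = 1.40.

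| Times averaged | Difference (mm) | r = 0.5: 95% CI, p | r = 0.8: 95% CI, p |
|---|---|---|---|
| All eight | 4.13 | −0.77 to 9.04, 0.097 | −1.77 to 10.03, 0.17 |
| Session 1 | 2.79 | −2.06 to 7.63, 0.26 | −2.81 to 8.39, 0.32 |
| Session 2 | 5.48 | −0.09 to 11.05, 0.054 | −0.93 to 11.88, 0.092 |

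**Step 4: why r of 0.5 to 0.8.** Suppose the Table 4 letters are Tukey results over four times within each group and session. The threshold is then 3.69 × √(MSE/35), where 3.69 is the 5% studentized-range point for 4 means and 3 × 34 = 102 df. Under equal correlation, MSE is the mean variance minus r times the mean product of SD pairs.
- Control, session 1: MSE = 239.9 − 217.6r. The letters separate 8.26 from 2.91 (gap 5.35) but not 8.09 from 2.91 (gap 5.18), which needs r of about 0.76 to 0.79.
- Dexamethasone, session 1: MSE = 125.5 − 89.1r. Separating 5.06 from 0.37 (gap 4.69) needs r of about 0.77 or more.
- Dexamethasone, session 2: MSE = 165.9 − 112.0r. Separating 7.57 but not 6.46 from 1.14 (gaps 6.43 and 5.32) needs r of about 0.5 to 0.8.
- Control, session 2: no useful limit.

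The within-group reading is itself an assumption. In session 1 a gap of 5.18 counts as not different in control while 4.69 counts as different with dexamethasone. One common error term with 35 per arm could not give both.

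**Step 5: NRS.** Six of the eight Table 3 cells have identical medians and quartiles in both groups. In session 2 up to 1 h the median is 1 with dexamethasone and 0 with control. In session 2 up to 24 h the upper quartile is 2 with control and 1 with dexamethasone. There is no consistent direction.

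**Step 6: what cannot be computed.** Worst scores per volunteer cannot be recovered from the tables.

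**The case against.** The pointwise displays are not a departure from the Methods. Mann-Whitney tests at assessment points are what is described for NRS, the Table 4 labels may be Tukey results from the named ANOVA, and separate analysis by session is also described. The sentence in the Results is limited to assessment points and sessions, the table footnotes say only that no significant difference was found, and intensity is not the primary outcome. All of this stands. It does not rescue the word similar, because the single-point intervals in Step 2 are themselves wide.

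Two stronger readings are tempting, and the documents support neither.
- A reader might infer that a planned analysis was replaced by weaker ones. The documents show only that results were not reported. The ANOVA group effect is not named as a planned contrast, and the test named for overall intensity is Fisher's exact test.
- A reader might infer that a significant benefit is hidden. Eight means in one direction from the same volunteers are not eight independent signs. An overall p below 0.05 needs a common r below about 0.30, which the letters speak against. The letters do not limit the correlation between sessions. With r of 0.76 and 0.52 within sessions 1 and 2, a between-session value of 0, 0.1 or 0.2 gives p of about 0.04, 0.05 or 0.07, so only a value near zero would give significance. Session 1 alone gives p of 0.089 or more at every r from 0 to 1.

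The t approximation is also rough: the SD exceeds the mean in 15 of the 16 VAS cells. The documents give no threshold for a VAS difference that matters.

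**Conclusion.** The point holds as a missing result and an unsupported conclusion. The VAS data are inconclusive. The average difference is 4.13 mm (43% of the control mean, 4.13/9.66), with p of about 0.10 to 0.17. The 95% CI includes zero, and its upper limit of 9.0 to 10.0 mm is about as large as the control mean of 9.66 mm. That shows neither benefit nor similarity, and the NRS medians do not settle it. These figures rest on equal correlation of 0.5 to 0.8 between all eight scores, on the within-group Tukey reading of the Table 4 letters, and on a t approximation to skewed data. That similarity has not been shown does not depend on them: it follows from the absence of a margin and of any interval. The reported overall risk is not affected.

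**What to change.** 1. Report the already-calculated worst-score intensity by group, for NRS and VAS, with a between-group difference and 95% CI. A method suited to ordinal or skewed data, such as Mann-Whitney with a Hodges-Lehmann estimate, would serve. State that this differs from the Fisher's exact test named in the Statistical analysis section, and say which test was actually used.
2. Name the ANOVA factors and report the group and group-by-time results with CIs.
3. Give exact p-values for the 16 pointwise comparisons and label them descriptive.
4. In the Results, replace the word similar with a statement that no significant difference was detected, if the analyses in 1 and 2 bear that out, followed by the estimate and interval.

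Cost: further analysis of data already collected, with no dropouts, and a change of wording. This is a free improvement.

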### Materials and Methods

The scientific review committee and the committee for the protection of human participants of the local university (protocol number 1.376.881) approved this clinical investigation. It was registered in the clinical trials gov registry under the identification number NCT02956070. We performed this study using the protocol that the Consolidated Standards of Reporting Trials (CONSORT) statement established. Based on pre-established criteria, we selected 70 volunteers for this study. The study was performed from February 15, 2016, to July 12, 2016.

Two weeks before the bleaching procedures, each volunteer received a dental prophylaxis with pumice and water in a rubber cup and signed an informed consent form.

Study design: This was a randomized, triple-blinded, parallel-group clinical trial in which the volunteer, operator, and evaluator were blinded to the group assignment. A third researcher, not involved in the evaluation process, was responsible for the administration of the drugs. The study was carried out in the clinics of the School of Dentistry of Fluminense Federal University (Nova Friburgo, RJ, Brazil). Patients were recruited as they seek for treatment in the clinics of Dentistry of both Universities. No advertisement was made for participant recruitment. Patients were recruited in the order in which they reported for the screening session, thus forming a sample of convenience.

Inclusion and exclusion criteria: Volunteers included in this clinical trial were at least 18 years old, had good general and oral health, and did not report any type of TS. The volunteers were required to have 8 caries-free maxillary anterior teeth without restorations, be free of periodontal disease and review and sign the informed consent form. The central incisors had to be shade A1 or darker as judged by comparison with a value-oriented shade guide (VITA Classical, VITA Zahnfabrik). Despite the fact that the color shade A1 is one of the lightest colors measurable using VITA Classical, many volunteers with A1 shade teeth seek dental bleaching, as they are dissatisfied with the color of their teeth.

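### The statement that tooth sensitivity lasted no longer than 48 hours is unsupported: ratings stop at 48 hours, and the last row of scores is not zero

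*Combined protocol and SAP*

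**What the plan says.** In the combined protocol and SAP, the Tooth Sensitivity paragraph of the Results draws a conclusion on duration from Tables 3 and 4: "the bleaching-induced TS did not last longer than 48 hours after the bleaching protocol".

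The rating schedule is in Materials and Methods, TS evaluation: "TS was evaluated during bleaching and up to 1 hour, 24 hours and 48 hours postbleaching". On the VAS, "0 = no sensitivity and 100 = severe sensitivity". The same section sets the rule for absence of sensitivity: "If the volunteer scored 0 (no sensitivity) in all time assessments from both bleaching sessions, this volunteer was considered to be insensitive". Any other pattern counts as sensitivity.

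Tables 3 and 4 follow this schedule, and their last row in each session is the up-to-48-h row. On follow-up, the Results say: "All volunteers attended the recall visit 1 week postbleaching". The Methods describe shade evaluation at 1 week, but neither the Methods nor the tables give a TS rating for that visit.

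**The concern.** The sentence puts an upper limit on how long TS lasts. Ratings that stop at 48 h can support such a limit only if every volunteer scored 0 at the last one. If some did not, the end of their sensitivity was not observed.

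TS is the trial's main outcome, and its duration is something readers may repeat to patients. The sentence carries no qualification and refers to the tables as its evidence, so it matters whether those tables can bear it.

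**Working it through.** The 48-hour limit does not come from a formula, so there is no calculation of the plan's to reproduce. The check has two parts: what was rated, and what the last row implies.

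**1. Schedule against claim**

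| Source | TS ratings |
|---|---|
| Materials and Methods, TS evaluation | during bleaching; up to 1 h, 24 h and 48 h |
| Tables 3 and 4 | the same four rows per session, none later |
| 1-week recall | attended by all; no TS rating described or tabulated |

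Nothing rated after 48 h is available to show that TS had ended.

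**2. Is the last row zero?**

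Inputs:
- Group size n = 35, from Table 2 (33 + 2 control, 28 + 7 dexamethasone). This agrees with the total ("we selected 70 volunteers for this study") and with the absence of dropout ("No discontinuity in both treatment groups was found in the clinical investigation").
- Up-to-48-h VAS mean (SD), from Table 4: session 1, control 2.91 (9.14) and dexamethasone 0.37 (1.54); session 2, control 1.91 (5.46) and dexamethasone 1.14 (4.46).
- VAS scores cannot be negative.

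Formulas:
- Sum of scores: S = n × mean
- Sum of squares: Q = (n − 1) × SD² + n × mean²
- If k volunteers score above 0, the Cauchy-Schwarz inequality gives S² ≤ k × Q, so k ≥ S²/Q.

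Worked case, control, session 1:
- S = 35 × 2.91 = 101.85
- Q = 34 × 9.14² + 35 × 2.91² = 3136.73
- S²/Q = 101.85²/3136.73 = 3.31, so at least 4 volunteers

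| Session, group | S (mm) | Q | S²/Q | Minimum above 0, of 35 |
|---|---|---|---|---|
| 1, control | 101.85 | 3136.73 | 3.31 | 4 |
| 1, dexamethasone | 12.95 | 85.43 | 1.96 | 2 |
| 2, control | 66.85 | 1141.28 | 3.92 | 4 |
| 2, dexamethasone | 39.90 | 721.80 | 2.21 | 3 |

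The minimum counts do not change if each mean and SD is moved by 0.005 in the direction that lowers the bound. They are lower bounds; the true counts may be larger.

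**3. Do the other results in the tables settle duration?**

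- Table 3 gives an NRS median of 0 (0-0) in all four up-to-48-h cells. A third quartile of 0 means that about three quarters or more scored 0. It leaves room for up to about a quarter above 0, which is compatible with the counts above.
- In every column of Tables 3 and 4 the up-to-48-h row carries the letter B and the up-to-24-h row the letter A. That shows a fall in intensity, not that TS had ended in every volunteer.

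**The case against.** The strongest reply is about the row label. It reads up to 48 h, so it may record pain over the interval since the 24-h rating and not pain at hour 48. A volunteer with pain at hour 30 and none at hour 40 would score above 0 and still fit the sentence. Even a spot reading of pain at 48 h would not show pain after 48 h.

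This stands, and it limits the point. A reader might infer from the four positive means that the trial's own table disproves the sentence, or that TS was still present at hour 48. The documents support neither. On the interval reading, the time at which TS ended is unknown for volunteers with a positive score. On the spot reading, TS was present at 48 h and its later course is unknown. Either way, the limit of 48 h was not observed.

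A reader might also look to the largest scores that the figures imply. The highest score in a cell is at least Q/S: 3136.73/101.85 = 30.8 mm for control in session 1, and by the same formula 6.6, 17.1 and 18.1 mm in the other cells. These are intensities at an unknown hour in the window. They say nothing about duration and do not measure the size of the error.

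It is also fair to say that this is one descriptive sentence, that no test or group comparison depends on it, and that the tables show openly where ratings stop. That limits the consequence but does not supply the missing evidence.

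One defence fails. The Results report no adverse effects, but that is not a TS rating. The same section reports two volunteers who took an analgesic for TS, so TS was evidently not counted there.

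**Conclusion.** The duration statement does not follow from the tables it cites. TS is right-censored at 48 h: nothing later is described as rated, and the last rated window contains positive VAS scores from at least 4, 2, 4 and 3 of 35 volunteers (control and dexamethasone in session 1, then in session 2). The statement is unsupported, not shown to be false. How long TS lasted beyond 48 h, if it did, cannot be derived from these documents.

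The counts assume 35 ratings per cell, non-negative scores, and printed SDs with divisor n − 1. The conclusion also assumes that no unreported TS rating was made at the 1-week recall. If one exists and was zero for everyone, it would show that TS had ended by then, but still not by 48 h.

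The fault lies in the wording of a result and not in any analysis. The absolute risk of TS, the intensity comparisons and the shade results are unaffected.

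**What to change.** Replace the sentence in Results, Tooth Sensitivity, with wording such as:

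> TS intensity was low on average in the up-to-48-h assessment (mean VAS 0.4 to 2.9 mm), with some volunteers in both groups reporting TS in this last rated window; TS after 48 h was not assessed.

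Add the number of volunteers in each group and session with VAS > 0 or NRS > 0 in that window, so that readers have actual counts and not lower bounds. It would also help to state whether the up-to-48-h rating refers to the interval since 24 h or to the moment of rating.

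The cost is one sentence and a count from data already collected, with no reanalysis. The statement becomes somewhat less favourable.

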During bleaching	8.09 (17.06) AB	7.51 (15.46) A	NS†	14.03 (21.39) A	6.46 (6.34) AB	NS†
Up to 1h after bleaching	11.14 (20.08) A	6.31 (12.78) A	NS	14.31 (20.13) A	7.57 (13.46) A	NS
Up to 24h after bleaching	8.26 (13.48) A	5.06 (9.86) A	NS	16.60 (21.57) A	9.77 (20.55) A	NS
Up to 48h after bleaching	2.91 (9.14) B	0.37 (1.54) B	NS	1.91 (5.46) B	1.14 (4.46) B	NS

\* Within each column, significant differences are represented by different uppercase letters.

† NS: No significant difference between groups.

TABLE 5

Means (standard deviations) of the change in shade guide units obtained with the VITAL Classical\* and VITA Bleachedguide 3D-Master\* at baseline versus each bleaching session and 1 week post-bleaching.

COLOR	GRO	DUPS		MEAN DIFFERENCE
EVALUATION TOOL	Control	Dexamethasone	P VALUE	(95% CONFIDENCE INTERVAL)
VITA Classical	2.14 (1.52)	1.89 (1.37)	0.46	0.35 (-0.43-0.95)
VITA Bleachedguide	1.91 (0.95)	1.86 (0.97)	0.81	0.06 (-0.40-0.52)
VITA Classical	0.74 (1.15)	0.71 (1.49)	0.93	0.03 (-0.61-0.66)
VITA Bleachedguide	1.29 (0.52)	1.23 (0.69)	0.70	0.06 (-0.23-0.35)
VITA Classical	2.54 (2.39)	2.91 (1.96)	0.48	-0.37 (-1.42-0.67)
VITA Bleachedguide	3.00 (1.19)	3.2 (1.35)	0.51	-0.20 (-0.81 -0.41)
VITA Classical	2.77 (1.96)	2.26 (1.87)	0.27	0.51 (-0.40-1.43)
VITA Bleachedguide	3.20 (1.13)	3.09 (1.17)	0.68	0.11 (-0.44 – 0.66)

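### Non-significant difference tests on colour change are reported as matching equality between groups, but equivalence was not tested and the VITA Classical interval leaves a sizeable loss of whitening open

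*Combined protocol and SAP*

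**What the plan says.** The Statistical analysis section says that between-group colour changes, from baseline to one week after the second session, "were compared by using a t test". It adds: "In all statistical tests, the significance level was 0.05". It does not say whether the colour tests are one- or two-sided, and it sets no equivalence or non-inferiority margin for colour. The Sample size calculation names the absolute risk of tooth sensitivity as the primary outcome and sizes the trial on that alone.

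Under Color Evaluation in the Results, the between-group findings ("VITA Classical: P = 0.27; VITA Bleachedguide 3D-MASTER: P = 0.68") are said to have "matched the hypothesis of equality between the groups after bleaching". The next sentence points to the effect size and confidence interval in Table 5 and says that this "is evidence of no statistical difference between groups".

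**The concern.** Equality is the null hypothesis of a t test. Failing to reject it means that no difference was detected. It does not favour equality over the other values that the data also allow. A claim of similarity needs either a prespecified equivalence or non-inferiority test, or a reading of the confidence limits. The document plans no such test, and its Results text does not discuss the limits.

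What is at stake is the conclusion about whitening. A reader of the Results paragraph alone would take it that the two groups whitened equally. The paragraph also summarises whitening as about 3 units in both groups, although the final VITA Classical means are 2.77 (control) and 2.26 (dexamethasone). The reader cannot learn from the text how much lost whitening the VITA Classical data leave open.

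**Working it through.** **Inputs.** Means (SD) of the overall change come from Table 5. The table's row labels are not legible in the available text, so the rows were identified by the P values 0.27 and 0.68 given in the Results.

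| Guide | Control | Dexamethasone | Printed difference (95% CI) | Printed P |
|---|---|---|---|---|
| VITA Classical | 2.77 (1.96) | 2.26 (1.87) | 0.51 (-0.40 to 1.43) | 0.27 |
| VITA Bleachedguide | 3.20 (1.13) | 3.09 (1.17) | 0.11 (-0.44 to 0.66) | 0.68 |

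There are 35 participants per arm (Table 2: 33 + 2 and 28 + 7), and the Results report no dropouts. The difference is control minus dexamethasone (2.77 - 2.26 = 0.51), so a positive value means less whitening with dexamethasone.

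**Step 1: reproduce the printed results.** SE = sqrt(SD1²/35 + SD2²/35); 68 degrees of freedom, two-sided 95% critical value 1.9955.

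- VITA Classical: SE = sqrt((3.8416 + 3.4969)/35) = 0.458. t = 0.51/0.458 = 1.11, P = 0.269. CI = 0.51 ± 0.914 = -0.40 to 1.42.
- VITA Bleachedguide: SE = sqrt((1.2769 + 1.3689)/35) = 0.275. t = 0.11/0.275 = 0.40, P = 0.69. CI = 0.11 ± 0.549 = -0.44 to 0.66.

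Both agree with Table 5 within rounding. They also show that two-sided tests fit the printed P values and intervals.

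**Step 2: express the limits as a share of control whitening, treating the control mean as fixed.**

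- VITA Classical: loss up to 1.43/2.77 = 52%; gain up to 0.40/2.77 = 14%. The point estimate is 0.51/2.77 = 18% less.
- VITA Bleachedguide: loss up to 0.66/3.20 = 21%; gain up to 0.44/3.20 = 14%.

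**Step 3: allow for sampling error in the control mean.** Fieller's 95% interval for the ratio R = dexamethasone/control solves (mC² - t²vC)R² - 2·mC·mD·R + (mD² - t²vD) = 0, with v = SD²/35.

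- VITA Classical: 7.236R² - 12.520R + 4.710 = 0, so R = 0.55 to 1.18: a loss of up to about 45%.
- VITA Bleachedguide: 10.095R² - 19.776R + 9.392 = 0, so R = 0.81 to 1.15: a loss of up to about 19%.

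**Step 4: what the sample size could show about colour.** The documents give no important difference in SGU, so the values here are assumptions.

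- Power to detect 1 SGU with 35 per arm, by normal approximation, is Φ(1/(SD·sqrt(2/35)) - 1.96). With the pooled SD of 1.915 on VITA Classical this is Φ(0.22) = 59%. With 1.15 on VITA Bleachedguide it is Φ(1.68) = 95%.
- Against illustrative non-inferiority margins of 0.5, 1.0 and 1.5 SGU, the VITA Classical upper limit of 1.43 fails the first two and passes the third. The VITA Bleachedguide limit of 0.66 fails at 0.5 and passes at 1.0.

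Any claim of equivalence would therefore depend on a margin that the plan does not set. Correcting the wording needs none, only the limits already printed.

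**The case against.** The strongest reply is that the verb in the Results means only consistent with the null hypothesis. The following sentence sends the reader to the confidence interval and claims no more than the absence of a statistical difference. Means, SDs, P values and intervals are all printed in Table 5, colour is not the primary outcome, and a t test is an acceptable way to compare colour change.

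Much of this stands. It limits the point to wording, and nothing in the planned analysis has to change. But the milder sentence does not withdraw the reference to equality, and neither sentence discusses the limits.

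Two stronger readings are tempting, and the documents do not support them:

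- A reader might infer that the document declares equality proven, or states outright that dexamethasone leaves whitening unimpaired. It uses neither form of words and sets no non-inferiority objective for colour.
- A reader might infer from the upper limit that dexamethasone reduces whitening. The interval includes zero and also allows 0.40 SGU more whitening with dexamethasone. Another VITA Classical row in Table 5, whose time point is not legible, has a difference of -0.37 (-1.42 to 0.67), in favour of dexamethasone.

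It is also fair that the size depends on the guide and on the scale. VITA Bleachedguide is much tighter. The Color evaluation section concedes that the VITA Classical scale is not strictly linear, so a percentage of mean SGU is only approximate.

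**Conclusion.** The equality statement is wrong as written, with minor severity because it concerns the conclusion on a non-primary outcome. The trial detected no difference in whitening. It did not test equivalence and was not sized for colour. On VITA Classical, a loss of about 45% (Fieller) to 52% (control mean fixed) of control whitening is not excluded. On VITA Bleachedguide, the loss is at most about 19% to 21%. Both intervals also include more whitening with dexamethasone, so the result is uncertainty and not evidence of harm.

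These figures assume 35 analysed participants per arm, two-sided tests, the rows of Table 5 identified by their P values, and the document's own treatment of shade units as approximately linear. Whether the VITA Classical interval is too wide to be useful cannot be settled from the documents, because they name no important difference.

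**What to change.** In the Results, under Color Evaluation, delete the phrase about the hypothesis of equality. Replace it and the sentence after it with:

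> No significant difference in whitening was detected. The mean difference (control minus dexamethasone) was 0.51 SGU (95% CI -0.40 to 1.43) on VITA Classical and 0.11 SGU (95% CI -0.44 to 0.66) on VITA Bleachedguide; equivalence was not tested, and on VITA Classical a loss of up to 1.43 SGU with dexamethasone cannot be excluded.

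Keep the t test and Table 5 as they are. Do not add an equivalence margin now: the results are known, and the choice of margin would decide the answer.

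The cost is wording only, with no new data or analysis. The conclusion on whitening becomes weaker.
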